**5.0 Outcome Characteristics and Endpoint Definitions:**

For Phase 1, we will determine if any participants report adverse reactions or any side effects from the TI-NDBS stimulation, using the Stimulation Experience Scale questionnaire. Some potential side effects include itching, unusual sensations, abnormal or unpleasant thoughts, or physical sensations. We will follow-up with participants after the stimulation session to determine if there were any side effects from TI-NDBS. For phase 2, we will measure the change in neural activity for each target area of the brain to be stimulated for TI-NDBS vs. no stimulation to determine if the activity is different for TI-NDBS stimulation, again using the Stimulation Experience Scale. For phase 3, we will determine whether TI-NDBS vs. sham leads to a difference in nicotine craving via self-report measures and corresponding reduced nicotine vapor inhalation in the MRI scanner. For phase 4, we will determine a difference in nicotine craving via self-report measures and corresponding reduced nicotine vapor inhalation in the MRI scanner between TI-NDBS and tDCS. We will also examine differences in neural activity measured by fMRI between TI-NDBS and tDCS.

## **6.0 Statistical Analysis and Sample Size:**

In phase 1, we will assess tolerability with an initial cohort of 3 stimulation subjects. Our aim here is to identify any potential adverse effects, using two approaches. We will monitor the stimulation condition for clinically significant adverse effects such as seizures, prohibitive pain, etc, though we do not expect this based on all the literature from earlier studies.

In phase 2, we will conduct a pilot assessment to determine whether and how the stimulation immediately influences neural activity. As this is a within-subjects pilot design intended to estimate the effect size of neural activation, we will scan 10 subjects, comparing the neural activation in each subject during the stimulation period with neural activation in the same subject during the no-stimulation periods. We do not have a power analysis for this phase yet, because the whole point is to perform a pilot study in order to estimate the effect sizes. We anticipate that 10 subjects will be sufficient to estimate the effect sizes.

In phase 3, we will proceed in two parts. During the first pilot part, we will recruit 5 subjects in each of 3 groups, to identify which two of the three candidate brain regions seem most promising sites of stimulation to reduce nicotine craving and consumption. Once we identify the two more promising sites of stimulation, we will proceed to the second part. We do not have a power analysis for this part because again, we are looking to estimate the relative effect sizes for one stimulation site compared to another. For the second part, we will recruit 45 subjects who are heavy smokers into three groups of 15 each, then ask them to abstain from smoking for several hours prior to the session. The first group will receive TI-NDBS over the most promising site. The second group will receive TI-NDBS over the second most promising site. The third group will receive sham stimulation. We will measure total real-time ad lib nicotine vapor inhalation during a 60 minute stimulation session, and every ten minutes, we will ask subjects to

self report their level of craving on a Likert scale of 0-10. We will identify whether TI-NDBS over the insula or nucleus accumbens is more effective than sham stimulation. We will then follow up with subjects 1 week afterward, using ecological momentary assessment (EMA) via smartphone apps (ilumivu.com) to assess cigarette use and craving. We expect to find that TI- NDBS reduces craving and cigarette consumption relative to sham. **Analysis and predictions:** We predict that TI-NDBS will outperform tDCS at reducing smoking and cigarette craving, which in turn will outperform sham stimulation. We will sum the total inhaled nicotine vapor over the 60 minute session and perform pairwise t-tests to determine if total drug intake is lower with one of the stimulation groups vs. sham. Also, we will average the self reported craving levels across each subject during the 60 minute session, and we will perform pairwise tests to determine if stimulation lowers self reported craving. During the 7 days following the stimulation session, we will give subjects the ilumivu app on their smartphones (or a loaner phone if needed), and we will notify them daily to request a self report of their level of craving and cigarette use in the preceding 24 hours. We will average these measures for each subject and perform an omnibus ANOVA (time point by group), followed by post-hoc pairwise tests to determine whether the stimulation led to longer lasting effects relative to sham. We will perform post-hoc tests for each of the 7 days to identify any differences in the duration of stimulation effects. For a power analysis, we do not yet know how many subjects will be necessary to achieve statistical power in the second part of phase 3, because we do not yet know what the effect sizes are. Nevertheless we anticipate that 15 subjects per group will provide a solid estimate of the effect sizes of stimulation relative to sham, so that we can write a grant to scale up the number of subjects based on a power analysis.

In phase 4, we will compare TI-NDBS vs. conventional transcranial direct current stimulation for smoking reduction. To test this, we will recruit another 45 subjects who are heavy smokers into three groups of 15 each, then ask them to abstain from smoking. The first group will receive standard transcranial direct current anodal stimulation of the right DLPFC and cathodal stimulation of the left DLPFC (F3 and F4 in the 10/20 system). The second group will receive TI-NDBS to the most promising site as determined in phase 3. The third condition will be sham. We will assess craving levels every 10 minutes during the 60 minute stimulation period. We will repeat this for five consecutive days. We will then follow up with subjects 1 week after starting the tDCS, using ecological momentary assessment (EMA) via smartphone apps (ilumivu.com) to monitor cigarette use and craving. We will compare the sham vs. tDCS vs. TI-NDBS groups to identify differences in craving and relapse. **Analysis and predictions:** We expect to find that TI-NDBS leads to reduced craving and drug use relative to sham or tDCS. We will carry out the same statistical tests as in Study 1. As before, we do not yet know the effect sizes but will aim to estimate them based on the initial 45 subjects.

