**Phase 2. Neural effects.** In Phase II, subjects will complete the MRI safety screen questionnaire and the stimulation experience scale (the same scale from phase 1) prior to entering the MR scanner. The electrodes (2 cm x 2 cm) will be attached and subjects will enter the MR scanner and the TI-NDBS stimulation will be administered while in the scanner, alternating 2-minute stimulation and 2-minute no-stimulation periods. Subjects may alternatively receive stimulation from all electrodes at the same frequency in order to make comparisons to temporal interference stimulation. For every two minute period of stimulation, the current will increase slowly at a constant rate for 30 seconds until it reaches the appropriate intensity. At the end of the stimulation, the current will decrease slowly for 30 seconds until it reaches zero. For sham stimulation, the current will increase during a 30 second interval and then immediately decrease back to zero over a 30 second interval, for a total of 60 seconds of stimulation. This will allow us to identify immediate neural activation due to stimulation, while controlling for any scalp sensations with the sham condition. The electrodes will be placed to target stimulation at either anterior Cingulate or nucleus accumbens. Immediately following the stimulation session, subjects will complete the stimulation experience scale and then will clean off residual electrode gel. The stimulation experience scale is administered again 30 minutes later. The subject will be in the scanner for about 1 hour.

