#### New technology.

Temporally-interfering non-invasive deep brain stimulation (TI-NDBS) is a form of transcranial alternating current stimulation (tACS) which allows focal stimulation and disruption of deep brain structures, without invasive measures, and without disrupting overlying brain regions (Grossman et al., 2017, Cell). Temporal interference tACS (TI-NDBS) has been used since at least the 1970s in humans to treat pain, and devices and software to stimulate the human brain with temporal interference tACS is now FDA approved for investigational use and sold commercially <https://soterixmedical.com/research/interferential-stimulation>.

TI-NDBS works by applying two or more alternating current electric fields to the scalp at frequencies above those necessary to cause stimulation (e.g. 2KHz). The field frequencies differ by a small amount (e.g. 2000 Hz vs. 2010 Hz), so that the differences causes a 10 Hz beat frequency where the fields overlap, similar to the beat frequency of two guitar strings which are slightly out of tune with each other. The location can be tuned to anywhere in the brain, and with any beat frequency, even within deep structures (Figure 1, from Grossman et al., 2017). In our study, subjects will also receive stimulation from all electrodes at the same

Indiana University, Bloomington, IN

frequency (e.g. 2000 Hz) in order to make comparisons to temporal interference stimulation (e.g. 2000 Hz vs. 2010 Hz).

As the technology is very new, we do not yet have sufficient data to estimate an effect size of TI-NDBS on nicotine or opiate use or craving. We specifically hypothesize that tDCS neurostimulation to the dorsolateral PFC will reduce nicotine intake and craving, and that TI-NDBS to the insula will be more effective than tDCS at reducing both nicotine intake and craving. The electrodes will be placed according to the standard EEG 10/20 system.

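### Phase 2 includes sham to control for scalp sensation, but its endpoint and analysis compare stimulation only with no stimulation

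*Combined protocol and SAP*

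**What the plan says.** **Design (section 3.0, Phase 2).** Subjects are scanned while 2-minute stimulation and 2-minute no-stimulation periods alternate. Sham is described separately: the current ramps up over 30 seconds and "then immediately decrease back to zero over a 30 second interval, for a total of 60 seconds of stimulation". The stated aim is to identify activation due to stimulation "while controlling for any scalp sensations with the sham condition". The same paragraph adds an optional comparator: "Subjects may alternatively receive stimulation from all electrodes at the same frequency".

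**New technology.** This text names no phase and is firmer about that comparator: "In our study, subjects will also receive stimulation from all electrodes at the same" frequency, for comparison with TI.

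**Endpoint (section 5.0).** The Phase 2 outcome is worded as follows: "we will measure the change in neural activity for each target area of the brain to be stimulated for TI-NDBS vs. no stimulation".

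**Analysis (section 6.0).** Ten subjects are scanned in a within-subject pilot, "comparing the neural activation in each subject during the stimulation period with neural activation in the same subject during the no-stimulation periods". Its declared purpose is to estimate effect sizes. No power calculation, test or significance level is given for Phase 2.

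For Phase 2, neither 5.0 nor 6.0 mentions sham or same-frequency stimulation.

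**The concern.** The plan itself treats scalp sensation as something to be controlled, and that is its stated reason for including sham. The Phase 1 description warns that subjects may feel tingling or see flashing lights, and section 5.0 lists itching and unusual sensations among possible side effects. In the no-stimulation periods there is no current and nothing to feel. The contrast named in 5.0 and 6.0 therefore leaves in the component that the design set out to remove.

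Two conclusions are at stake. One is the effect size, which section 6.0 gives as the reason for running Phase 2. The other is whether stimulation reached its target, since the phase overview in section 2.0 calls Phase 2 a localization study. A response to sensation in the cingulate or accumbens could be taken for either.

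**Working it through.** The plan states no figure to reproduce for this point. The check sets the sections side by side and asks what each available contrast would estimate.

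**1. Is sham the same thing as no stimulation?** No. Section 3.0 describes them separately, and sham delivers 30 + 30 = 60 seconds of current. Sham cannot be read into the no-stimulation periods of 5.0 and 6.0.

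**2. What does each contrast contain?** For a given target area, let *A* be the effect specific to the TI beat, *C* any other effect of the current on the brain, and *S* the response to feeling an active block.

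| Contrast | Contents | Named for Phase 2 in 5.0 or 6.0? |
|---|---|---|
| TI − no stimulation | *A* + *C* + *S* | Yes, the only one |
| TI − sham | *A* + *C* + *S*, less whatever sham itself produces | No |
| TI − same-frequency | *A*, plus any sensation caused by the beat itself, if current and ramps are equal | No |

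**3. How closely does each control match?** Section 3.0 sets one ramp rule for active blocks: "For every two minute period of stimulation, the current will increase slowly at a constant rate for 30 seconds", with a 30-second ramp down at the end. It does not say whether the ramps fall inside the 2 minutes. The time at full current in an active block is therefore:

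- both ramps inside: 120 − 30 − 30 = 60 seconds
- ramp down afterwards: 120 − 30 = 90 seconds
- both ramps outside: 120 seconds

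Sham has ramps and no plateau, so its time held at full current is 0. It matches the onset and offset of sensation but not 60 to 120 seconds of sustained sensation. Same-frequency blocks are the closer match. The New technology text says the carriers run "at frequencies above those necessary to cause stimulation", so on the plan's own premise these blocks carry the scalp current without the beat.

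**4. Would more subjects help?** No. With *n* = 10, the 95% confidence interval for a mean within-subject difference has half-width *t*(0.975, 9)/√10 = 2.262/3.162 = 0.72 standard deviations of the paired differences. A larger *n* shrinks that width, but the interval stays centred on *A* + *C* + *S*.

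**5. What might a control contrast cost in precision?** Assume independent block noise of unit variance, *N* stimulation blocks and *N* rest blocks, and all stimulation blocks currently TI. The block-noise standard error is then:

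- TI − no stimulation: √(1/*N* + 1/*N*) = √(2/*N*)
- blocks split equally between TI and one control: √(2/*N* + 2/*N*) = √(4/*N*), a ratio of √2 = 1.41
- blocks split equally over TI and two controls: √(3/*N* + 3/*N*) = √(6/*N*), a ratio of √3 = 1.73

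These are upper bounds. If control blocks are already scheduled, the added cost is smaller. Variation between subjects is not affected by this calculation.

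**6. Who receives the controls?** No section says which Phase 2 subjects receive sham or where its blocks fall. On same-frequency stimulation, section 3.0 is optional where the New technology text is definite.

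**The case against.** The best defence is that this is one combined document. Section 3.0 states the sham control and its purpose, so the bias arises only if 5.0 and 6.0 are read without it. That is correct as far as it goes: a reader might infer that Phase 2 has no control for sensation, and the documents do not support that. What remains is that the two sections defining the estimate state a specific contrast, and it is not the one the design says it will deliver.

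A second defence is that stimulation versus no stimulation answers whether stimulation does anything at all, and that neither 5.0 nor 6.0 claims a sensation-free effect. This also stands, and is why the contrast is worth keeping as a description. It cannot support a TI-specific claim.

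Third, the consequence is small. A reader might infer that a biased Phase 2 would misdirect the later phases. The documents do not support that. Section 6.0 gives site selection to Phase 3 part 1, electrode placement comes from finite element modelling, and the effect sizes for the later grant come from Phase 3 part 2 against sham.

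Fourth, nothing shows that sensation activates the Phase 2 targets. The background links bodily sensation and pain to the insula, whereas Phase 2 targets the cingulate or accumbens. This is a fair limit: the bias is a reasonable possibility, not a demonstrated one.

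**Conclusion.** The concern holds as a mismatch between design and analysis. If 5.0 and 6.0 are followed as written, the Phase 2 effect size combines any TI effect with any response to feeling the current, although the design includes sham for that very purpose.

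The textual gap is certain. The size of the bias is unknown, because no document gives the response to sensation in either target. It may be tempting to convert the ramp times into a percentage of sensation left uncontrolled, or into a false-positive rate. Both would need a model of sensation and a standardized effect that the documents do not supply.

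A reader might also take the New technology text as a promise of same-frequency blocks in Phase 2. It names no phase, and the only wording specific to Phase 2 is optional.

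The harm is confined to the effect-size and target-engagement conclusions of a 10-subject pilot. The text should be corrected before the Phase 2 data are analysed, but the later phases do not depend on it.

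**What to change.** - In sections 5.0 and 6.0, name the within-subject TI minus sham difference, and TI minus same-frequency wherever those blocks are given, each with a 95% confidence interval, as the estimates on which any claim of a TI-specific effect rests.
- Keep TI minus no stimulation as a descriptive contrast.
- Reconcile the Phase 2 paragraph of section 3.0 with the New technology text on whether same-frequency stimulation is given.
- State which Phase 2 subjects and blocks receive sham.
- Note as a limitation that sham has ramps and no plateau, and so matches sustained sensation only partly.

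**Cost.** Text and analysis only, for subjects who already receive the control blocks. Contrasts between active and control blocks may be less precise, within the bounds shown in the working. If some subjects are not already due to receive a control, adding those blocks is a design change that uses scan time; otherwise that contrast rests on fewer than 10 subjects and should be reported as such.

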right insula. Another group will receive TI-NDBS over the nucleus accumbens. Another group will receive TI-NDBS to the anterior cingulate cortex. We will not target these brain areas in any particular order. Prior to stimulation, subjects will be administered a questionnaire to assess their physical experiences and sensations using a 5-point Likert-scale. Subjects will also be given the Nicotine Dependence Syndrome Scale to assess baseline Nicotine Dependence. In addition, we will measure total real-time ad lib nicotine vapor inhalation during a 60 minute stimulation session. At the start of the stimulation, the current will increase slowly at a constant rate for 30 seconds until it reaches the appropriate intensity. At the end of the stimulation, the current will decrease slowly for 30 seconds until it reaches zero. Every ten minutes, we will ask subjects to self-report their level of craving on a Likert scale of 1-10. We will identify whether TI-NDBS to the insula or nucleus accumbens or cingulate is more effective stimulation at decreasing cravings. In the second stage of Phase 3, we will take the two most promising of the three brain regions and repeat the procedure of stage 1, but with a larger sample size. The third group will receive sham stimulation as a control. In both stages, immediately after stimulation, subjects will complete the stimulation experience scale and then again 30 minutes later. We will then follow up with subjects every day, up to three times per day, for a period of 1 week afterward using Ecological Momentary Assessment (EMA) via a smartphone app (LifeData) to monitor cigarette and/or vaping use and craving. The questions that will be used in the app are in a script attached (see EMA follow up questions). In Phases 1, 2, and 4 subjects are paid \$25/hr. In Phase 3, subjects are paid \$40/hr. In addition, in Phases 3 and 4, subjects are paid \$5/day for providing ecological momentary assessment data outside of the lab sessions, and \$10 bonus for completing 7 consecutive days of ecological momentary assessment (EMA). Payment will be made at the end of each day's lab session in cash, and for phase 3, by check after the EMA period ends.

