conventional transcranial direct current stimulation for smoking reduction. To test this, we will recruit another group of subjects who are heavy smokers into three groups, then ask them to abstain from smoking. Prior to stimulation, subjects will be given the NDSS to determine baseline nicotine dependence. The first group will receive standard transcranial direct current anodal stimulation of the right DLPFC and cathodal stimulation of the left DLPFC (F3 and F4 in the 10/20 system). The second group will receive TI-NDBS to either the nucleus accumbens or anterior insula or anterior cingulate, depending on which is found to be more effective in Phase 3. The third condition will be sham. The strength of the stimulation and duration will be the same as in previous phases. Prior to stimulation, subjects will be administered a questionnaire to assess their physical experiences and sensations using a 5-point Likert-Scale. Immediately after stimulation, subjects will complete the stimulation experience scale, then complete the scale again 30 minutes later. In addition, we will assess craving levels every 10 minutes during the stimulation period. We will repeat this for five consecutive days. We will then follow up with subjects every day, up to three times per day, for 1 week after starting the tDCS, using EMA via a free smartphone app (ilumivu.com) to monitor cigarette use and craving. The questions that will be used in the app are in a script attached (see EMA follow up questions). We will compare the sham vs. tDCS vs. TI-NDBS groups to identify differences in craving and relapse. We expect to find that TI-NDBS leads to reduced craving and drug use relative to sham or tDCS. The procedure in this phase will not add anything new, except testing subjects with tDCS in addition to TI-NDBS and sham.

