### **Recruitment:**

Participants are recruited by placing flyers around the community that ask for responses from “heavy smokers who are interested in research and are between the ages of 18-50 years”. Participants are also recruited via Craigslist using a post titled “Participants Needed for Psychology Study.” After calling or emailing the lab, interested participants complete a 5 minute phone screen to determine eligibility (e.g., smoking at least 15 cigarettes per day). These phone screens will be de-identified and retained to show eligibility to participate. Once in the laboratory participants also complete the nicotine dependence severity scale to quantify the severity of their nicotine dependence. [name] and Brown have successfully recruited populations of heavy smokers for fMRI studies in the past. Subjects who express interest by calling or emailing the lab will be contacted via telephone by the lab subject coordinator. They will be asked a series of screening questions to confirm that they meet the inclusion/exclusion requirements. This screening interview will be oral and no information will be recorded or retained, as it is for screening purposes only. If subjects meet the inclusion criteria, they will then be asked to provide a schedule of availability and placed on a list of interested subjects. They will be informed that they may or may not be offered a spot in our current study, depending on available timeslots and how many participants we will run in relation to how many interested respondents we have. As volunteers are needed for specific time slots, the research coordinator will contact them to schedule them, and the first subject that is available for the required session time will be scheduled. Interested participants who meet all screening criteria but who are not offered a slot in our current study will be informed that they have the option to be put on our contact list for future studies. Previously interested volunteers will be removed from the contact list immediately if they so request.

[figure not shown]

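### Phase 3 compares total inhaled nicotine by unadjusted t-tests and gives the baseline NDSS no analysis role; adjusting for it may narrow the effect-size estimate at negligible cost

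*Combined protocol and SAP*

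**What the plan says.** Section 6.0 sets the size of the second part of Phase 3: "we will recruit 45 subjects who are heavy smokers into three groups of 15 each". Two groups receive temporal interference (TI) stimulation at different sites and the third receives sham. For the intake outcome the plan says: "We will sum the total inhaled nicotine vapor over the 60 minute session and perform pairwise t-tests". It names no covariate, stratification factor or baseline comparison.

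The baseline measure is in 3.0 Design. For Phase 3: "Subjects will also be given the Nicotine Dependence Syndrome Scale to assess baseline Nicotine Dependence". For Phase 4: "Prior to stimulation, subjects will be given the NDSS to determine baseline nicotine dependence". The Recruitment text gives a descriptive purpose under a slightly different name: "participants also complete the nicotine dependence severity scale to quantify the severity of their nicotine dependence". Neither 5.0 nor 6.0 mentions the scale.

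There is no power calculation: "we do not yet know how many subjects will be necessary to achieve statistical power in the second part of phase 3". Section 6.0 instead expects 15 per group to give a solid estimate of the effect against sham, for use in a later grant application. Phase 4 has the same size ("we will recruit another 45 subjects who are heavy smokers into three groups of 15 each") and its analysis is given by reference: "We will carry out the same statistical tests as in Study 1". The term Study 1 is not defined; presumably it means Phase 3.

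**The concern.** Ad lib intake by an abstinent smoker plausibly depends on how dependent that smoker is. If so, differences in dependence between subjects add noise to the comparison of arms, and a pre-stimulation measure can remove part of that noise. The plan collects such a measure and leaves it out of the analysis.

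This bears on the phase's own purpose. With no power claim, 15 per group rests on how well the effect size is estimated. The planned interval extends 0.75 SD either side of the estimate. That is wider than the only effect size the documents cite, d = 0.71 for five days of tDCS on cigarette consumption (3.0 Design). A later trial sized from so wide an interval inherits its uncertainty.

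**Working it through.** The plan has no power or precision figure to reproduce, so the check starts from the stated design.

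**Inputs.** From section 6.0: three arms of 15 (N = 45) and pairwise t-tests. Not in the documents, so assumed: two-sided 95% intervals, equal variances, and r over a range. The SD of intake is not given, so results are in SD units.

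**Standard error.** Difference between two arms of 15: √(2/15) = 0.365 SD.

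**Without the covariate.**
- Planned two-arm t-test, 28 df: 2.048 × 0.365 = 0.748 SD.
- Three-arm model without covariate, 42 df: 2.018 × 0.365 = 0.737 SD.

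Pooling the arms therefore accounts for about 0.01 SD of narrowing by itself. The fair comparator for the covariate is 0.737.

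**With the covariate, three arms, 41 df.** The variance factor is (1 − r²) × (1 + 1/40). The second term is the average cost of estimating the slope, with 40 = 45 − 3 − 2. Half-width = 2.0195 × 0.365 × √factor. Equivalent subjects per arm = 15/factor.

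| r | Variance factor | Half-width (SD) | Equivalent n per arm |
|---|---|---|---|
| 0 | 1.025 | 0.747 | 14.6 |
| 0.2 | 0.984 | 0.732 | 15.2 |
| 0.3 | 0.933 | 0.712 | 16.1 |
| 0.5 | 0.769 | 0.647 | 19.5 |
| 0.6 | 0.656 | 0.597 | 22.9 |

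**Break-even.** Against the three-arm model without covariate, half-widths are equal when (1 − r²) × 1.025 = (2.0181/2.0195)², which gives r ≈ 0.16. Against the planned two-arm t-test, the adjusted model is no wider even at r = 0 (0.747 v 0.748).

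**Power, for scale only.** At d = 0.71, a figure for a different treatment and outcome, the planned t-test has 47% power. The adjusted three-arm model has 47% at r = 0, 50% at r = 0.3 and 58% at r = 0.5.

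**Chance imbalance, if allocation is random.** The probability that a TI arm and sham differ by more than 0.5 SD in baseline NDSS is P(|Z| > 0.5/0.365) = 17%. By simulation with a shared sham arm, it is 29% for at least one of the two TI arms. At r = 0.5, a 0.5 SD imbalance moves the unadjusted difference by 0.5 × 0.5 = 0.25 SD. The unadjusted standard error already contains this variability, so it is not a gain on top of the table.

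**The case against.** A reader might infer that the plan certainly throws away precision. The documents do not support that. They give no correlation between NDSS and session intake, and without one the gain cannot be known. Section 4.0 excludes anyone smoking less than three quarters of a pack a day, which may narrow the range of dependence and lower r. That rule sets a floor and no ceiling, and it does not restrict NDSS itself, so dependence can still vary. At r = 0.3 the covariate's own contribution is 0.737 to 0.712, about one subject per arm. This objection stands, and it makes the benefit conditional.

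A reader might also infer that the unadjusted comparison is biased by imbalance in dependence. Under random allocation it is not; it is a valid estimate with a wider interval. Sections 3.0 and 6.0 describe no method of allocation, so the 17% and 29% rest on an assumption. If allocation were not random, imbalance could be larger, but the documents do not show that it is.

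The choice of NDSS can be questioned too. Breath carbon monoxide is measured as an index of recent smoking (3.0 Design) and also has no analysis role; after a few hours' abstinence it may predict intake as well. The documents do not settle which is better. NDSS is the measure explicitly placed before stimulation, and that supports it as the default.

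Finally, the Phase 4 procedures describe craving ratings during sessions on five consecutive days. Intake there rests on the general methods text, section 5.0 and the undefined Study 1. Extending the model to Phase 4 therefore needs a per-subject summary that the plan does not yet define.

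**Conclusion.** The point holds as a conditional one. The intake analysis in Phase 3 part 2 is unadjusted, a baseline dependence score is collected, and no analysis uses it. Relative to a three-arm model without covariate, adjustment narrows the half-width from 0.737 SD to 0.712, 0.647 or 0.597 SD at r = 0.3, 0.5 or 0.6, which is like having about 16, 19.5 or 23 subjects per arm. It brings no gain below r of about 0.16. These figures assume equal variances, a linear relation with a common slope, and two-sided 95% intervals.

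The change is worth making because the risks are lopsided: at r = 0 the interval is still no wider than the planned t-test's, while a moderate r gives a useful gain. It would be wrong to read it as a remedy for the sample size: at r = 0.5 the half-width is still about 0.65 SD.

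**What to change.** In section 6.0, replace the pairwise t-tests on total inhaled nicotine in Phase 3 part 2 with one pre-specified linear model of arm plus baseline NDSS score, fitted to all three arms. Report the same contrasts against sham with 95% intervals, and show the unadjusted differences as a check. State which NDSS score is used, and reconcile the two names given to the scale. The same covariate can enter the analysis of EMA-reported cigarette use.

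For Phase 4, apply the model to intake where it is measured, with one summary per subject over the five sessions, defined in advance. Replace the reference to Study 1 with the phase meant.

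The cost is a short addition to 6.0, one degree of freedom, and at most about 2.5% more variance in the estimate if r is near zero. No new visit, instrument or subject is needed.
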